Non-profit observational study on the role of the community pharmacist and the "pharmacy of services" in the case management of the diabetic patient.

1.1 Background and rational of the Study

Over the last few years, the Italian National Health Service has witnessed numerous and substantial changes, even more evident if one looks at the workload that this system is called to face when it comes to chronic diseases. In fact, while the progress of science has led to better outcomes in the treatment of acute diseases resulting in an increase in the average age of the population and an increase in the number of people suffering from chronic diseases, even multiple, on the other the changed socio-economic conditions activities have led to an increase in the number of elderly and socially fragile individuals. It takes very little to understand that these epidemiological and socio-sanitary mutations pose a serious threat to the stability of our health system.

To meet these new needs, the different countries of the world are analyzing and adopting various models of chronic disease management. Even if with different methodologies, all the models developed so far put the patient at the center of attention, in its uniqueness and with its needs, and propose to provide the latter with complete assistance, through the integration of health and social services.

In this scenario, also the role of pharmacist, historically linked to the dispensation of drugs upon presentation of a medical prescription and to a final control action to ensure a delivery of medicines in total safety, over time has evolved. In order to carry on this evolution, the pharmacist has been asked for new skills, to realize what has been defined as "the pharmacy of services", through which the pharmacist is recognized the possibility of becoming a strategic figure to meet the changed needs of the population on the one hand and the Italian National Health System on the other and to support the latter in the transition from a "waiting" medicine to an "initiative" medicine.

Diabetic disease and the resulting chronic complications, today, have a very significant impact on patients and their families, on morbidity and mortality, as well as having a strong economic impact on the health system. Despite this, most of the patients do not carry out what is foreseen by their

diagnostic therapeutic assistance path (PDTA) due to several reasons such as long waiting times, the need to move to undergo examinations, which is not so easy for young people of working age as well as older people, lack of homogeneity in access to care and in the provision of services and more. The community pharmacist, therefore, represents, for the position in which it is located within the Italian National Health Service, a potential not yet considered. In fact, it could take on the role of case manager (a professional who manages one or more cases entrusted to him according to a pre-established path, such as PDTA, in a defined space-time context) of the patient suffering from type 2 diabetes mellitus due to the capillarity territory, to the hourly availability superior to any other territorial health structure, to the health skills in its possession and to what it can offer in terms of services within the so-called "pharmacy of service". In this scenario, the pharmacist would not replace any of the other actors already present in the multidisciplinary care team but would integrate in the same and, moreover, being already an agreement with the Italian National Health Service, the conferral of this role would not cause a excessive increase in costs, such as that resulting from the hiring of new staff to achieve the same objectives.

2. Literature review

In the literature, the evidence relating to the pharmacist's involvement in chronic management of the type 2 diabetic patient is few and heterogeneous.

In the present studies (1-6), pharmacists working in hospital or primary care clinics, in first person or through telemedicine tools, are involved in providing educational sessions, performing therapeutic reconciliation and monitoring therapeutic adherence. In general, in each study where the pharmacist is given the opportunity to become an active part of the diabetic patient's care team, the improvement of therapeutic outcomes, recourse to hospitalization and the consumption of resources is evident. These effects are all the more evident when prescription skills are also recognized to the pharmacist, not provided for by current Italian legislation.

In literature, when we talk about telemedicine and pharmacists we often refer only to telemonitoring of glycemic values (7). Furthermore, telemedicine is seen as an advantageous tool only for rural and isolated areas, but its potential can also be appreciated in urban areas (8-10). In fact, from its use in the early diagnosis of complications and in the follow-up of diabetic patients it would result not only a reduction in the workload of health facilities that could devote more time to the care of those

patients who require more information than those who only need undergo a screening of the complications, but also a reduction of the costs related to the personnel and the infrastructures necessary to carry out the activities foreseen by the diagnostic therapeutic assistance plans. Moreover, the possibility of being able to undergo the necessary examination at any hour of the day, would certainly improve the adherence of the patients to the planned checks, a rapid identification of the complications and an early start of the necessary treatments.

On the other hand, clinical self-analysis equipment and telecarefertation systems (ecg, ocular fund, etc.) have reached maturity so that they can be used without reserve in the clinical management of patients.

The scenario at the base of the present study in which the contracted community pharmacist assumes the role of case manager of the patient suffering from type 2 diabetes mellitus and the pharmacy becomes the place where to perform the checks foreseen by the individual assistance plan in a flexible way (smart clinic), appears to have not been the subject of previous studies.

3. Study Objectives

Primary Endpoint

The primary objective of the study is the variation - compared to a historical cohort - of the percentage of adherence to PDTA (patients who performed the scheduled checks at 3-6-12 months / total of patients enrolled x 100) in the cohort of patients enrolled in the study and therefore followed by a case manager identified in the community pharmacist with the opportunity to perform the checks provided in telemedicine and self-analysis, thanks to the exploitation of the “pharmacy of service”.

Secondary Endpoints

The secondary objectives of the study are:

- variation in waiting times for the execution of the examinations envisaged by the PDTA;
- variation in levels of HbA1c, LDL-cholesterol, arterial pressure

- assessment of the economic impact secondary to the establishment of the figure of the Case Manager and the use of the “pharmacy of service”;
- assessment of the variation in the quality perceived by patients in carrying out this innovative treatment path, compared to the traditional model.

4. Study procedures

The study, whose duration will be 12 months (November 2018 - October 2019), which does not include any cost for the Italian National Health Service and for the same patients participating, is of type:

- observational
- prospective,
- single-center,
- no profit.

The following are the main phases of the research project.

Phase 1: Patient Enrollment (November 2018)

In the first phase, with a total duration of one month, patients are enrolled, presenting the characteristics indicated below, in a number equal to as a result of the detailed calculation in paragraph 8.

Phase 2: Review, database validation and definition of Individual Assistance Plan (December 2018)

In December 2018, the database is validated and the individual assistance plans defined by the general practitioners involved.

Phase 3: Case Management e follow up (December 2018- October 2019)

In the remaining months the Case Manager follows the patients in carrying out the checks provided by the reference PDTA and the Individual Assistance Plan drawn up by the attending physician.

ECG (performed with an electro cardiograph Microtel BT and reported by the HTN Srl power station), ocular bottom (performed with Nexty non-mydriatic fundus camera and reported by Next Sight Srl) and self-analysis (glycated hemoglobin, lipid profile and microalbuminuria, performed with Farmascreen device of Biochemical Systems International Spa) will be carried out directly in the pharmacy using the above mentioned reporting equipment and platforms. For the services requested that can not be carried out at the pharmacy, the pharmacist proceeds with the prescription from the General Practitioner, the booking of the exam by means of the CUP service and the execution of a telephone reminder service that reminds the patient when 'exam. Each performance is reported to the attending physician by sending the report in electronic format.

5. Study estimated duration

The study will last 12 months, from November 2018 to October 2019.

6. Inclusion and exclusion criteria

Recruitable patients:

- age > 18 years,
- patients with type 2 diabetes mellitus;
- able to express consent to the study
- regularly attending the trial site (Pharmacy [name] [name])

7. Case Report Form (CRF)

Electronic data collection forms are provided (Case Report Form - CRF) necessary for the collection of clinical information of the patient, together with those of an organizational and management nature.

The detail of the information to be collected is defined in the data collection forms.

For the purpose of a homogeneous data collection, for each patient belonging to the target population, a form is provided, whose structure generally foresees the following macro-areas:

- general information on the patient (ID, gender, age, etc.);
- near and remote pathological anamnesis
- vital parameters and input blood analysis

- examinations and procedures required for follow-up
- results and reports of the controls carried out during the follow up;
- perceived quality questionnaire.

8. Sample size and statistical analysis

Starting from the percentage of adherence to all the controls envisaged by the PDTA in a historical cohort described in the work carried out by the Emilia Romagna Region on the prevalent cases of 2015 (11) equal to 4%, a simple size of 20 patients is necessary to demonstrate the effectiveness of our intervention in order to increase the percentage of adhesion to 29%, with an error α of 0.05 and a statistical power (error $1-\beta$) of 95%. To avoid any dropouts or consensus withdrawals, the necessary sample was doubled to 40 patients.

The formula used to calculate the simple size is as follows:

$$N = \frac{p_0 q_0 \left\{ z_{1-\alpha/2} + z_{1-\beta} \sqrt{\frac{p_1 q_1}{p_0 q_0}} \right\}^2}{(p_1 - p_0)^2}$$
$$q_0 = 1 - p_0$$
$$q_1 = 1 - p_1$$
$$N = \frac{0.04 * 0.96 \left\{ 1.96 + 1.64 \sqrt{\frac{0.29*0.71}{0.04*0.96}} \right\}^2}{(0.29 - 0.04)^2}$$
$$N = 20$$

p_0 = proportion (incidence) of population
 p_1 = proportion (incidence) of study group
 N = sample size for study group
 α = probability of type I error (usually 0.05)
 β = probability of type II error (usually 0.2)
 z = critical Z value for a given α or β

The statistical analysis of the collected data will be developed through descriptive analysis.

The economic evaluation will be performed by comparing the costs incurred in the traditional path and the costs deriving from the application of the model under study, calculated with reference to the regional rate where appropriate.

The assessment of the perceived quality will be carried out through a short anonymous questionnaire administered at the end of the study to all the subjects enrolled.

All categorical variables measured in this study will be expressed as an absolute number and a percentage. Continuous variables will be expressed as mean and standard deviation or median and interquartile range [IQR], depending on the normal or non-data distribution.

The differences will be analyzed by chi-square tests, t-tests for unpaired data or by Mann-Whitney U tests, depending on the nature of the variable.

Any difference with a $p < 0.05$ will be considered statistically significant.

9. Results expected by the study

The problem of the poor adherence to the controls envisaged by the PDTA diabetes is a well-highlighted phenomenon but to which it is difficult to find a solution that gives tangible results in the short and long term, as can be seen from what can be found in the literature. The main causes of non-adherence reported in the aforementioned study (11) emerged from the focus groups conducted with patients and operators are the lack of a reference figure present continuously over time, motivating and able to give answers on several fronts (eg a nurses in group medicine and / or in the homes of health) and the difficulty of reconciling the management of the disease with the rhythms of life.

The present study by overcoming these critical issues, thanks to the use of the unexpressed potential of the “pharmacy of service” (remote execution of the services provided by the PDTA) and of the pharmacist, as a case manager, alongside the basic and specialist medicine, it will improve the current quality of care for type 2 diabetic patients (+ 25% adherence to the PDTA), with a view to sustainability.

10. Ethical Considerations

To protect privacy, the patients of the group described above will be identified only by means of progressive numerical codes (ID).

The data will be treated with confidentiality and confidentiality and disclosed only in aggregate and anonymous form.

The protection of subjects will be guaranteed as recommended in the Oviedo Convention (Convention for the Protection of Human Rights and the dignity of the human being in relation to the application of biology and medicine: Convention on Human Rights and Biomedicine - 4 April

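### The waiting-time endpoint has no rule for checks that were due but never done, so the planned comparison can understate, hide or in some scenarios reverse a real change

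*Combined protocol and SAP*

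**What the plan says.** Section 3 lists "variation in waiting times for the execution of the examinations envisaged by the PDTA" as a secondary endpoint. It gives no start date, unit of analysis or comparator for the wait.

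Section 8 gives general rules only. Continuous variables are summarised by mean and SD or by median and interquartile range. For comparisons, "The differences will be analyzed by chi-square tests, t-tests for unpaired data or by Mann-Whitney U tests", chosen by type of variable. There is no time-to-event method, no censoring rule, and nothing on checks that were due but not performed.

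Section 1.1 says that "most of the patients do not carry out what is foreseen by their" care pathway, "due to several reasons such as long waiting times" among other causes. Section 8 takes full adherence to be 4% in the historical cohort and targets 29%. Checks not done do count in the primary endpoint, which is "patients who performed the scheduled checks at 3-6-12 months / total of patients enrolled x 100".

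Section 7 has separate CRF areas for the examinations required and for the results of those carried out. Follow-up under Section 4, Phase 3, runs from December 2018 to October 2019, about 11 months.

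**The concern.** A wait that ends at execution is unobserved for a check that is never executed. At the end of follow-up only a lower bound is known. The t-test and the Mann-Whitney test need a value for each unit, so in the absence of another rule they would be run on executed checks alone.

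That selection is harmless only if it is unrelated to the wait. The protocol suggests otherwise on two counts: it names long waits as a cause of non-execution, and the intervention is meant to raise execution. The analysis would then condition on a post-intervention outcome, with different shares left out on the two sides. At stake is whether this endpoint can show the gain in access that the study hopes to find.

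**Working it through.** **The plan's own figures.** No figure is given for waiting time. The only calculated figure is the primary sample size: 0.04×0.96×{1.96 + 1.64×√(0.29×0.71/(0.04×0.96))}² / 0.25² = 20.37. The stated 20 reproduces (21 if rounded up). It does not bear on this endpoint.

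**Inputs.** From the documents: a follow-up window T of about 11 months. All waiting times and patient tolerances below are assumptions, and the results are illustrations only.

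**Step 1: loss by end of follow-up only.** Take exponential waits with median m, so λ = ln 2 / m, and assume the same window on both sides.
- Share executed: F = 1 − exp(−λT)
- Mean among executed: 1/λ − T·exp(−λT)/F
- Median among executed: −ln(1 − F/2)/λ

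For m = 12: 1/λ = 17.31 and F = 0.470. The mean is 17.31 − 11×0.530/0.470 = 4.92 and the median is 4.64 months.

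For m = 6: 1/λ = 8.66 and F = 0.719. The mean is 8.66 − 11×0.281/0.719 = 4.37 and the median is 3.86 months.

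The true gain of 6 months in the median appears as 4.64 − 3.86 = 0.78 months. The true gain in the mean, 17.31 − 8.66 = 8.65 months, appears as 4.92 − 4.37 = 0.55. With medians of 6 and 3 months, the means among executed checks are 4.37 and 3.39. The direction is kept in both examples.

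**Step 2: patients also give up.** Take lognormal waits and tolerances (log-SD 0.8), with a check executed only if its wait does not exceed the patient's tolerance or 330 days. Without the cap, the share executed is Φ(ln(tolerance median / wait median)/(0.8√2)). For wait 90 and tolerance 60 this is Φ(−0.358) = 0.36. Simulation with 400,000 checks per side gave the following (days, traditional vs new):

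| True medians | Tolerance medians | Executed | Median among executed | All due checks done by day 90 |
|---|---|---|---|---|
| 90 vs 60 | 60 vs 60 | 36% vs 50% | 50.7 vs 38.8 (shrunk) | 29.5% vs 45.3% |
| 90 vs 60 | 60 vs 180 | 36% vs 83% | 50.6 vs 51.5 (hidden) | 29.4% vs 65.5% |
| 90 vs 60 | 30 vs 180 | 17% vs 83% | 38.9 vs 51.5 (reversed) | 15.2% vs 65.4% |
| 90 vs 30 | 30 vs 180 | 17% vs 94% | 38.7 vs 28.4 (shrunk) | 15.2% vs 88.9% |
| 90 vs 90 | 30 vs 180 | 17% vs 72% | 38.8 vs 70.3 (false worsening) | 15.2% vs 46.4% |

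**Step 3: the Mann-Whitney test.** With 40 due checks per side, true medians of 90 and 60 days, no cap and 2,000 runs, the test is significant in the right direction in 59% of runs when every check is executed. On executed checks only, with tolerances 60 then 180, it is 1.7% right and 3.2% wrong. With tolerances 30 then 180, it is 0.2% right and 12.6% wrong.

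**The case against.** The plan nowhere says that unexecuted checks are dropped. This is inferred from the endpoint's wording, the tests named and the absence of any other rule. Waiting time is undefined, and Section 4 has the pharmacist booking outside examinations through the CUP service. A wait from request to booked date would exist even for a missed appointment. That stands as a limit: the bias follows only if the wait ends at execution. The endpoint's wording points that way, though, the plan does not adopt the booking definition, and checks never booked would still be lost.

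A reader might infer from 4% and 29% that 96% and 71% of waits are missing. They are not. These are per-patient figures for completing all controls, and a patient who misses one check still contributes waits for the others. Assuming, for illustration, eight independent checks per patient, per-check execution would be 0.04^(1/8) = 67% and 0.29^(1/8) = 86%.

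Nor is a check never done necessarily one with a long wait. Sections 1.1 and 9 also cite travel, the lack of a continuous reference figure and the rhythms of life. If non-execution is unrelated to the wait and to examination type, executed-only medians are not biased.

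A reversal can also be built from examination mix alone. Take equal numbers of due checks, with 1-month examinations executed 80% vs 90% and 5-month examinations 20% vs 70%. The pooled mean goes from (0.8×1 + 0.2×5)/1.0 = 1.8 to (0.9×1 + 0.7×5)/1.6 = 2.75 months, with no wait changed. Reporting by type removes this, and the plan does not say that types are pooled. It supports reporting by type, not survival methods.

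Last, censoring merges persistence with service delay. The table's last row shows the day-90 share rising although the true waits are equal. This stands: the repaired endpoint is time to execution and must be labelled so.

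**Conclusion.** The concern holds as a conditional one. If the wait ends at execution, the planned summaries and tests have no place for checks not done, and the protocol's own premises make that selection likely to depend on the wait and to differ between the sides. A real change can be understated, hidden or, in some scenarios, reversed.

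Two stronger conclusions are not supported: that the comparison is certainly biased, and that reversal is to be expected. The endpoint is undefined, the documents give no waiting times, and reversal needed a marked rise in patients' tolerance alongside a moderate true gain. With unchanged tolerance or a large gain, the effect shrank but kept its direction.

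The size is therefore unknown. A definition alone would not cure the problem if the wait ends at execution, because the named tests do not handle censored waits. One secondary endpoint is affected; the primary endpoint and its sample size are not.

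**What to change.** - Define the wait as the time from request, or from the due date under the Individual Assistance Plan, to execution. Name the comparator.
- Keep every due check listed in the CRF. Censor those not executed at withdrawal or end of follow-up, and state the assumption that withdrawal is unrelated to the wait.
- Report by examination type the Kaplan-Meier estimate and the percentage of due checks executed by fixed times within the roughly 11 months of follow-up, with intervals that allow for clustering by patient.
- Make a formal comparison only if the comparator has the same data on unexecuted checks. Otherwise describe the study cohort, give the number of due checks without a wait, set executed-only figures against executed-only comparator figures by examination type, and state the limitation. A Kaplan-Meier median that includes unexecuted checks should not be set against a comparator figure that may cover executed examinations only.

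The cost is a paragraph of analysis text, two dates per check (which the detailed CRF forms may already hold) and slightly more analysis. The real downside is that a formal comparison may prove impossible, since the documents identify no waiting-time comparator.

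### Late HbA1c and LDL-cholesterol values depend on attending the checks that form the primary endpoint, and the plan has no same-patient comparison or rule for unmeasured patients

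*Combined protocol and SAP*

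**What the plan says.** - **Endpoint.** Section 3 names "variation in levels of HbA1c, LDL-cholesterol, arterial pressure" among the secondary objectives. It gives no time point, comparator or analysis population.
- **Primary endpoint.** Section 3 defines adherence as "patients who performed the scheduled checks at 3-6-12 months / total of patients enrolled x 100". Patients who skip checks stay in this denominator.
- **Source of follow-up values.** In Section 4, Phase 3, "the Case Manager follows the patients in carrying out the checks provided by the reference PDTA and the Individual Assistance Plan". In the same phase, "self-analysis (glycated hemoglobin, lipid profile and microalbuminuria, performed with Farmascreen device of Biochemical Systems International Spa) will be carried out directly in the pharmacy". No separate study assessment is described.
- **Data collected.** Section 7 lists "vital parameters and input blood analysis" at entry and, for follow-up, "results and reports of the controls carried out during the follow up".
- **End of study.** The only assessment that Section 8 sets for everyone is a "short anonymous questionnaire administered at the end of the study to all the subjects enrolled". It includes no blood test.
- **Analysis.** Section 8 gives means or medians, and chi-square, unpaired t or Mann-Whitney tests. It gives no paired analysis and no rule for missing values.
- **Planning figures.** Adherence is 4% in the historical cohort, and the sample is sized "in order to increase the percentage of adhesion to 29" per cent. The calculated 20 patients are doubled to 40 to cover dropouts and withdrawals.

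**The concern.** A check that is not done yields no value. Whether a patient contributes a late HbA1c or LDL therefore depends on the behaviour that the study measures as its main outcome. The primary endpoint keeps non-attenders in its denominator, but nothing keeps them in the metabolic endpoint.

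Two separate errors can follow.

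1. **Composition.** If entry values of all enrolled are compared with follow-up values of attenders by an unpaired test, the two groups are not the same patients. The difference then mixes a change in level with a change in who was measured.
2. **Selective change.** Even with a same-patient comparison, the mean change describes attenders. It differs from the change in all enrolled whenever unmeasured patients changed by a different amount.

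A metabolic result for the pharmacy model could then not be separated from the pattern of attendance.

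**Working it through.** **The plan's own figure.** With p0 = 0.04, p1 = 0.29 and the printed z values 1.96 and 1.64:

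N = 0.0384 × {1.96 + 1.64 × √(0.2059/0.0384)}² / 0.25² = 20.37

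This agrees with the stated 20 (strict rounding up gives 21). The sample size is not in dispute; 29% and 40 are the inputs used below.

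**Coverage.** Let f be the share of enrolled patients with a late HbA1c or LDL value. The documents do not give f. At the target, 0.29 × 40 = 11.6 patients complete every check and about 28 miss at least one. A patient who misses only another examination can still have a late HbA1c, so 29% is a floor for f if the target is met. The upper limit is 40 of 40.

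**Error 1, composition.** Unpaired difference = (follow-up mean, measured) − (entry mean, all)
= (mean change in measured) + (1 − f) × (entry mean in measured − entry mean in unmeasured).

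Each point of difference in entry mean therefore shifts the result by 0.71, 0.50, 0.30 or 0.10 points at f = 29%, 50%, 70% or 90%. A within-patient comparison removes this term.

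**Error 2, selective change.** Change in all enrolled = f × (change in measured) + (1 − f) × (change in unmeasured), so
bias = (1 − f) × (change in measured − change in unmeasured).

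Pairing does not remove this term. Assume that HbA1c changes by −0.5 points in measured patients and, in unmeasured patients, either by 0 or by +0.3. All three values are assumptions.

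| f | Patients measured | Reported change | All enrolled, unmeasured 0 | Overstatement | All enrolled, unmeasured +0.3 | Overstatement |
|---|---|---|---|---|---|---|
| 29% | 11.6 | −0.50 | −0.145 | 0.355 | +0.068 | 0.568 |
| 50% | 20 | −0.50 | −0.25 | 0.25 | −0.10 | 0.40 |
| 70% | 28 | −0.50 | −0.35 | 0.15 | −0.26 | 0.24 |
| 90% | 36 | −0.50 | −0.45 | 0.05 | −0.42 | 0.08 |
| 100% | 40 | −0.50 | −0.50 | 0 | −0.50 | 0 |

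The bias is zero at any f if measured and unmeasured patients change equally. It reverses sign if unmeasured patients improve more.

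**The case against.** The strongest reply is that coverage may be high. HbA1c and lipids are measured in the pharmacy itself, and Section 6 requires patients to attend that pharmacy regularly. The adherence figure covers all controls in the care pathway, so a patient can fail it on an ECG, a fundus examination or an examination booked elsewhere. This stands: 29% is a worst case at the target, and full coverage with no bias is possible. A reader might infer that only about 12 of 40 patients will have a late value; the documents do not support that.

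A second reply is that attenders being better controlled is a composition effect, which pairing removes, and that such patients may have less room to improve. This also stands. A reader might infer that an observed fall would come entirely from who was measured, or that the bias must favour the model. The documents fix neither.

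Third, the plan does not say that all entry values will be compared with attenders' follow-up values, or that the result will be read as the cohort change. Section 7 describes only general areas of the data form and leaves the detail to forms that are not reproduced. This limits the point to what the text permits: an unrestricted objective, unpaired tests and no rule for unmeasured patients.

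Finally, this is a secondary endpoint in a 40-patient study whose analysis is described as descriptive. That lowers the stakes but does not remove the need to say whom the result describes.

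**Conclusion.** The point holds in limited form. In the protocol as written, a late HbA1c or LDL value exists only if the check was attended, and attendance at the scheduled checks is the primary outcome. Following Section 8 literally can mix a change in level with a change in who was measured. A paired analysis would cure the composition error but would still describe attenders only.

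On an assumed 0.5-point difference in HbA1c change, the bias runs from 0.355 points at f = 29% through 0.05 at f = 90% to 0 at full coverage. These figures rest on the assumed difference and on a coverage that the plan does not state; they illustrate the possible size and are not a forecast.

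The point is confined to HbA1c and LDL. A reader might extend it to blood pressure, but the protocol does not say where follow-up blood pressure values come from.

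**What to change.** In Section 8:

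- Define the HbA1c and LDL endpoint as within-patient change from entry to the last scheduled check (12 months in Section 3), in patients with both values.
- Report the number measured out of all enrolled.
- Show entry values separately for patients with and without a follow-up value.
- Label the result as applying to patients who attended the check.
- Add a sensitivity range for all enrolled, for example no change and a worsening in unmeasured patients. No change should not be the headline: it is itself an assumption, and it is not conservative if unmeasured patients worsen.

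A closing HbA1c and lipid measurement for all enrolled is optional. If added, it should be obtained after the primary adherence endpoint has been determined and never counted toward adherence. With enrolment in November 2018 and the study ending in October 2019, a test to which everyone is called at study end would coincide with the 12-month check and could raise the primary endpoint.

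The analysis changes need only text in Section 8 and no new data. The optional measurement would need a protocol change and further use of a pharmacy test already in the study. The downside is that the stated conclusion becomes narrower and the change in all enrolled may look smaller.

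### Does doubling 20 to 40 for dropouts fail to protect the 95% power, given that the primary endpoint divides by all enrolled patients?

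*Combined protocol and SAP*

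**What the plan says.** Section 3 defines the primary endpoint as "the variation - compared to a historical cohort - of the percentage of adherence to PDTA". It is calculated as the patients who performed the scheduled checks at 3, 6 and 12 months, divided by the "total of patients enrolled x 100". A patient who withdraws therefore stays in the denominator and, without the later checks, cannot enter the numerator.

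Section 8 takes historical adherence as 4% and states that "a simple size of 20 patients is necessary to demonstrate the effectiveness of our intervention". The target is given by "in order to increase the percentage of adhesion to 29" percent, "with an error α of 0.05 and a statistical power" of 95%. One sentence then moves from 20 to the enrolment figure: "To avoid any dropouts or consensus withdrawals, the necessary sample was doubled to 40 patients".

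The plan states no expected dropout rate. It does not say in so many words whether 29% describes enrolled or retained patients, and it has no separate rule for counting withdrawals beyond the endpoint formula.

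**The concern.** Raising a required size n to n/(1 − d) for a dropout fraction d is sound when dropouts are removed and n patients remain to be analysed. Doubling is that formula with d = 0.5. The section 3 denominator removes nobody. Under it, dropout leaves the analysed number at 40 and may lower the adherence rate being tested. If so, the step from 20 to 40 does not describe the planned analysis, and 95% power is not guaranteed at the loss that the doubling seems to allow for.

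A second risk concerns the analysis. An analyst who followed the logic of the doubling might take withdrawals out of the denominator, and this can matter. Suppose 20 of 40 patients withdraw and 4 complete all checks. Against 4%, 4/40 gives z = 1.94 and an exact upper-tail p of 0.075, whereas 4/20 gives z = 3.65 and p = 0.007. The same data would lead to opposite conclusions.

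**Working it through.** **Inputs.** From section 8: p0 = 0.04, p1 = 0.29, two-sided α = 0.05 (z = 1.96), power 95% (z = 1.64), 20 patients doubled to 40. From section 3: denominator = all enrolled. Assumption, not in the plan: a loss fraction d, varied from 0 to 0.5.

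**The plan's own figure.** N = p0q0{1.96 + 1.64√(p1q1/p0q0)}² / (p1 − p0)².
- p0q0 = 0.0384 and p1q1 = 0.2059, so √(0.2059/0.0384) = 2.316.
- The bracket is 1.96 + 1.64 × 2.316 = 5.758.
- N = 0.0384 × 5.758² / 0.0625 = 20.4, which the plan gives as 20.

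Solved for power, the formula is Φ{[(p1 − p0)√N − 1.96√(p0q0)] / √(p1q1)}. It gives 94.7% at N = 20.

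**Reading A: 29% is the rate among all enrolled.** Losses are already inside the 29%, so N = 40 and p1 = 0.29.
- Plan's formula: 99.6%.
- Exact binomial: the smallest cutoff with upper tail at most 0.025 under 4% is 5 of 40 (tail 0.021). P(X ≥ 5 | 40, 0.29) = 99.6%.

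**Reading B: 29% is the rate among retained patients, and every withdrawal counts as non-adherent.** The tested rate becomes 0.29(1 − d), still with N = 40 and a cutoff of 5.

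| Loss d | Tested rate | Power, exact | Power, plan's formula |
|---|---|---|---|
| 0% | 29.0% | 99.6% | 99.6% |
| 10% | 26.1% | 98.9% | 99.0% |
| 20% | 23.2% | 97.1% | 97.5% |
| 25% | 21.75% | 95.5% | 96.3% |
| 30% | 20.3% | 93.0% | 94.6% |
| 40% | 17.4% | 84.9% | 88.9% |
| 50% | 14.5% | 70.7% | 78.7% |

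Power reaches 95.0% at d of about 26% (exact) and about 29% (plan's formula). With 40 enrolled, 26% is 0.26 × 40 = 10.4 patients, so the target survives the loss of about 10.

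**Like-for-like comparison at 50% loss.** The plan's 95% comes from a normal approximation, while 70.7% comes from an exact rule. Under the same exact rule, 20 patients with no dropout need 4 or more responders and have 87.4% power. The fall is therefore from 94.7% to 78.7% by the formula, or from 87.4% to 70.7% by the exact rule. Setting 95% against 71% mixes the two methods.

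**The case for a change.** The strongest argument for a change is that the doubling sentence fits neither reading. If 29% applies to all enrolled, no dropout allowance was needed. If it applies to retained patients, the allowance was worked out on the wrong principle. One clarifying sentence would cost nothing, and the 4/40 against 4/20 example shows that the choice of denominator can reverse the primary conclusion. Withdrawal may also be related to adherence, because completing the checks is itself the outcome.

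Part of this stands. The rationale for 40 is poorly expressed, and naming a dropout rate and the population behind the 29% would be tidier. The denominator example has less force, because section 3 has already settled the matter: adherence is calculated over all enrolled. Only an analyst who departed from the written endpoint would report 4/20, and nothing in the plan directs that. The sample-size sentence concerns how many patients to recruit and does not define an analysis set.

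The 71% figure needs both a 50% loss and 29% being conditional on retention. The loss is only back-calculated from 20/40, and the sentence reads equally well as a generous margin. The conditional reading goes against section 3, where the percentage of adherence is an all-enrolled quantity, and section 8 uses the same term for its target.

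**Conclusion.** The concern does not call for a change. The mechanism is correct: with an all-enrolled denominator, withdrawals dilute the rate and do not reduce the number analysed, so the usual dropout inflation is not the proper justification for 40. The number itself is sufficient. Taking adherence as section 3 defines it, power is 99.6%. On the less natural retained-patient reading it is at least 95% for losses up to about 26% (exact) or 29% (plan's formula). It falls to 71–79% only at a 50% loss, which the plan nowhere states or expects.

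These figures treat the historical 4% as fixed, as section 8 does, and on the retained-patient reading they count every withdrawal as non-adherent. Enrolling 40 and dividing by 40 meets the stated power on the plan's own terms. Rewording the sentence would leave the sample size, endpoint and test as they are and would repeat a denominator already fixed. It is a gap in explanation that an analyst following section 3 fills without difficulty.
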